9.3.1 Full Analysis Set

The FAS and safety set are defined in the same way and will comprise all subjects who receive at least 1 dose of trial drug. Subjects will be analyzed according to the actual trial treatment received.

9.3.2 Safety Set

The safety set is equal to the FAS.

9.3.3 Response Evaluable Set

The response evaluable set consists of all subjects who have baseline evaluable disease according to RECIST 1.1 and at least 1 postbaseline disease assessment. It also includes subjects who die or are withdrawn from treatment due to clinical progression before the first response assessment; these subjects are treated as nonresponders.

9.3.4 Dose-Determining Set

The DDS will include all FAS subjects in the escalation part who meet the minimum exposure criterion and have sufficient safety evaluations or experience a DLT during the first 21 days of dosing (ie, in Cycle 1).

A subject will meet the minimum exposure criterion if the subject receives at least 80% of the preplanned dose of each trial treatment during the DLT period.

Subjects who do not experience a DLT during Cycle 1 (the first 21 days of dosing) will be considered to have sufficient safety evaluations if they have been observed for \geq 21 days following the first dose and are considered by both the sponsor and investigators to have enough safety data to conclude that a DLT did not occur. Subjects will be analyzed according to the trial treatment received, as defined for the FAS.

9.3.5 Pharmacokinetic Analysis Set

The PAS will include all subjects who receive at least 1 dose of trial drug and who provide at least 1 evaluable PK sample for GEN1053 in monotherapy and combination therapy. Refer to Table 1-3, Table 1-6, Table 1-10, Table 1-15 and Table 1-16 for further detail on sampling times.

9.3.6 Immunogenicity Analysis Set

The IAS will include all subjects who receive at least 1 dose of GEN1053 as monotherapy or combination therapy and have a baseline and at least 1 evaluable on-treatment (predose) ADA sample for GEN1053 as monotherapy or combination therapy.

Genmab

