PK/ADA sampling	8.5								See T	able 1-2					
Biomarkers	8.7								See T	able 1-3					

ADA= antidrug antibody; C=cycle; CT=computed tomography; d=D/day(s); ECG= electrocardiogram; ECOG PS=Eastern Cooperative Oncology Group performance status; MRI=magnetic resonance imaging; PK= pharmacokinetic(s); SFU1=safety follow-up visit 1; SFU2=safety follow-up visit 2; UNS=unscheduled.

a. For the last subject discontinuing treatment, there will be no survival follow-up and the last visit for that subject will be SFU 2.

b. Informed consent must be obtained prior to the screening period.

c. Visit window (+3d) applies to Cycle 2 Day 1 only.

d. Optional.

e. A physical examination and vital signs should only be performed as indicated by the subject's symptoms, adverse events, or other findings as determined by the investigator.

f. Temperature, blood pressure, and heart rate should be measured according to Table 1-4 on infusion days. On noninfusion days, vital signs should be obtained any time during the visit. g. Refer to Section 6.7.2.3 for details on post GEN1053 infusion precautions and observation periods.

h. All local laboratory samples at the screening visit must be obtained within 7 days prior to Cycle 1 Day 1 (with the exception of hepatitis B sample, which may be obtained earlier).

i. Local laboratory samples should be obtained on Day 1 of each cycle or no more than 3 days before the visit for Cycle 2 and beyond and reviewed before dosing.

Cycle/Visit	Screening		Сус	le 1		Cycle 2		Cycle 3		Cycles 4 to X	Treatment Discontinuation	SFU1	SFU2	UNS
Day	≤21 days prior to Visit C1 (D1)	D1	D3	D8	D15	D1	D1	D8	D15		-	30 days after last dose of trial treatment	60 days after last dose of trial treatment	-
Visit Window			+2d	±1d	±1d	+3d	±3d	±1d	±1d	±3d		+5d	±7d	
PK Sampling (Secti	on 8.5)													
Preinfusion (on infusion days)		x				х	х			х	х	x	х	xb
EOI + 5 min (+ 5 min)		x				х	х			х				
EOI + 2 hr (± 30 min)		x					х							
EOI + 4 hr (± 1 hr)		x												
EOI + 48 hr (+ 2 days)			x											
EOI + 168 hr (± 1 day)				х				х						
EOI + 336 hr (± 1 day)					х				х					
ADA Sampling (Sec	tion 8.8)			•								•		
Preinfusion (on infusion days)		x				х	х			X ^a	х	x	х	xb
ECG ^e (Section 8.3.4)													
Preinfusion (on infusion days)	x	x				х	x			x	х	x	x	xb
EOI (+ 15 min)		x				х								
EOI + 2 hr (±15 min)		x				х	x			х				

Table 1-2 PK, ADA, and ECG Sampling – Dose Escalation – GEN1053 Monotherapy

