ADA=antidrug antibody; C=cycle; ECG=electrocardiogram; D/d=day(s); EOI=end of infusion; hr=hours; min=minutes; PK=pharmacokinetic(s); SFU1=safety follow-up visit 1; SFU2=safety follow-up visit 2; UNS=unscheduled.

Note: Clock time must be recorded for infusion start and stop, and for each sample collected.

a. ADA sample at even-numbered cycles only.

b. Optional.

c. ECGs are to be taken as single assessments. From Cycle 5, ECGs must be obtained at Cycle 5, Cycle 7, and every 4 cycles thereafter (ie, Cycles 11, 15, etc.)

Confidential

Cycle/Visit ^a	Screening		Сус	le 1			Су	cle 2		Cycle 3	cle 3 Cycles 4 to X		Treatment Discontinuation	UNS
Day	≤21d prior to C1 (D1)	D1	D3	D8	D15	D1	D3	D8	D15	D1	D1	D 8	-	
Visit window		+3d	+2d	±1d	±ld	±3d		±1d	±1d	±3d	±3d	±1d		
Tumor biopsy	Xb							2	ζ ^b					X ^h
Cytokines		Xc	x	x		Xc	х	x		x				$\mathbf{X}^{\mathbf{h}}$
Immunophenotyping (whole blood)		x	x	x	x	x	x	x	x	x	Xe	X ^d	х	Xh
PBMCs		x		x	х	х		x	x	x	Xe	Xd	х	Xh
Proteomics (sCD27)		x												
ctDNA		x						ĺ		x			х	Xh
DNAseq		x												
Receptor occupancy		x	х	х	х	Х				х				
Complement (C3a and Bb)		Xf		x		Xf		x		Xg				

Table 1-3 **Biomarker Evaluation Schedule – Dose Escalation – GEN1053 Monotherapy**

C=cycle; ctDNA=circulating tumor-derived deoxyribonucleic acid; D/d=day(s); DNAseq= deoxyribonucleic acid sequencing; FFPE=formalin-fixed, paraffin embedded; PBMC=peripheral blood mononuclear cell; sCD27=soluble CD27; UNS=unscheduled.

a. All samples will be collected predose unless otherwise specified.

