premature sacrifice of several monkeys in the studies. Some plasma biomarkers, including transaminase levels, indicated associated liver function changes. Because of these adverse effects, the monkeys in the GLP study at 5 and 30 mg/kg could be dosed only once.

• Due to adverse findings at all dose levels, the NOAEL or HNSTD for GEN1053-induced adverse effects could not be determined in the pivotal GLP toxicology study.

In a series of in vitro studies with human and/or cynomolgus monkey blood cells or tissues, it was shown that GEN1053 only binds to tissues known to express CD27 (T cells, NK cells, induced B cells); in particular, no binding of GEN1053 to red blood cells, platelets, megakaryocytes, or megakaryoblasts was detected. When incubated with human whole blood, GEN1053 did not induce cytokine release, hematological changes, hemolysis, or clumping/precipitation in the plasma.

The mechanism behind the adverse hematological effects observed in the cynomolgus monkey toxicology studies (thrombocytopenia, coagulation changes, anemia, bleeding, etc) is uncertain. Possible mechanisms could be platelet aggregation caused by GEN1053-induced ADAs that were rapidly cleared due to immune complex formation and thus not detected, or CD27-related exaggerated pharmacology affecting the lymphoid cells and bone marrow function at the high dose levels employed in the monkey studies.

A more detailed description of the nonclinical safety findings for GEN1053 is provided in the IB.

Based on the findings in nonclinical safety studies with GEN1053, a very cautious approach for the FIH clinical trial with GEN1053 has been implemented to ensure proper observation, handling and mitigation of potential toxicities detected in the nonclinical safety program:

- CCI
- A cautious dose-escalation procedure for the initial part of the FIH clinical trial
- Close monitoring of hematology and coagulation systems as well as of hepatic function and PK characterization in the subjects (including RBC/Hb, PLT, APTT/PT, ALT, CRP, complement factors (C3a and Bb), PK, and ADAs)

Further details on mitigation of potential toxicities are provided in Section 2.3.

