 - o Grade 3 IRRs that resolve to \leq grade 1 within 24 hours.
 - Grade 3 anorexia when grade 2 anorexia was present at baseline or that lasts for <14 days after the last trial treatment administration.
 - Grade 3 nausea/vomiting or diarrhea for less than 72 hours with adequate antiemetic and other supportive care
 - Grade 3 fatigue for less than 7 days
 - Grade 3 or higher electrolyte abnormality that lasts up to 72 hours, is not clinically complicated, and resolves spontaneously or responds to conventional medical interventions

The investigator must notify the medical monitor immediately of a DLT. Frequent laboratory monitoring of CBC including differential count should be initiated to document start and resolution of hematological AEs. All AEs occurring during the defined DLT evaluation period will be assessed according to the criteria above. All GEN1053 or GEN1053+IM related AEs will be monitored and included in the evaluation of the toxicity profile of GEN1053 or GEN1053+IM unless the event is clearly determined to be unrelated to trial treatment (eg, PD).

Subjects experiencing a DLT within the DLT evaluation period should discontinue trial drug immediately. If requested by the investigator, the sponsor may allow a subject with a DLT to continue in the trial. For this decision, a thorough benefit-risk assessment of the individual subject is required, and consultation of the DMC may be considered.

If a subject experiences a toxicity that would have qualified as a DLT, but occurs after the DLT evaluation period, the subject's benefit-risk must be thoroughly assessed. Continued treatment with GEN1053 and/or IM must be agreed between the sponsor and the investigator.

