9.4 Statistical Analyses

This section is a summary of the planned statistical analyses of the most important endpoints including primary and key secondary endpoints. The SAP will be finalized prior to database lock, and it will include a more technical and detailed description of the statistical analyses described in this section.

Baseline is the last available measurement prior to first dosing of trial treatment, if not otherwise specified.

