9.4.3 Safety

9.4.3.1 Adverse Events

For all safety analyses, the FAS (which is identical to the safety set) will be used.

The overall observation period will be divided into 3 mutually exclusive segments:

- 1. Pretreatment period: from day of subject's informed consent to the day before first dose of trial medication
- 2. On-treatment period: from day of first dose of trial medication to 30 days after last dose of trial medication
- 3. Posttreatment period: starts when the on-treatment period ends

Summary tables for AEs will include only AEs that started or preexisting AEs that worsened during the on-treatment period (ie, TEAEs).

The incidence of TEAEs (new or worsening from baseline) will be summarized by system organ class and/or preferred term; intensity (based on grades of NCI-CTCAE version 5.0) (see Section 8.4.1); type of AE; relationship to each trial treatment.

SAEs, nonserious AEs, and AESIs during the on-treatment period will be tabulated.

All deaths (on-treatment and posttreatment) will be summarized.

All AEs, fatal AEs, AESIs, and SAEs (including those from the pre- and posttreatment periods) will be listed and those collected during the pretreatment and posttreatment period will be flagged.

Further summaries of AEs will be specified in the SAP.

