9.4.7 Immunogenicity Analyses

ADA titers to GEN1053 in monotherapy or in combination therapy will be separately listed and positive/negative host immune response to GEN1053 and presence of neutralizing antibodies may be summarized (positive/negative). The presence of PK concentrations above a certain threshold, which depend on the drug tolerance of the ADA assay at the same time as the ADA sample, may make the ADA undetectable and hence render nonconclusive. The association between positive/non-positive ADA, PK (predose, AUC, C_{max}) and safety findings will be explored.

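### As worded, the immunogenicity analysis set leaves out subjects who stop before the Cycle 2 Day 1 predose draw, so entry depends on early safety outcome

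*Combined protocol and SAP*

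**What the plan says.** Section 9.3.6 defines the IAS as subjects with at least 1 dose of GEN1053 who "have a baseline and at least 1 evaluable on-treatment (predose) ADA sample for GEN1053 as monotherapy or combination therapy". Section 9.4 fixes the baseline: "Baseline is the last available measurement prior to first dosing of trial treatment, if not otherwise specified". The Cycle 1 Day 1 preinfusion sample is therefore the baseline sample.

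Table 1-2 (monotherapy escalation) and Table 1-10 (HNSCC expansion) have the same ADA pattern: preinfusion at Cycles 1, 2 and 3, then "ADA sample at even-numbered cycles only", plus treatment discontinuation, SFU1 and SFU2, with an optional unscheduled sample. Neither schedules an ADA draw between Cycle 1 Day 1 and Cycle 2 Day 1.

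Section 6.7.1 gives the default after a DLT: "Subjects experiencing a DLT within the DLT evaluation period should discontinue trial drug immediately". The sponsor may allow an exception at the investigator's request.

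Section 9.4.7 says that the association of ADA status with PK "and safety findings will be explored". It names no analysis set, and it warns that circulating drug can hide ADA. On the monkey thrombocytopenia, Section 2.2.2.1 states: "Possible mechanisms could be platelet aggregation caused by GEN1053-induced ADAs that were rapidly cleared due to immune complex formation". It offers exaggerated CD27 pharmacology as the alternative and calls the mechanism uncertain.

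**The concern.** An analysis set for immunogenicity should not depend on how well the subject tolerated the first dose. Here it does. To have a postbaseline predose sample, a subject must reach the Cycle 2 Day 1 visit, and toxicity in Cycle 1 is one of the main reasons for not reaching it.

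This matters more here than in many first-in-human trials. Immunogenicity is a secondary objective. Thrombocytopenia and bleeding are the adverse events of special interest (Section 8.4.1.1), and Section 8.4.3.5 says that they will be watched for any relevance of the nonclinical findings to humans. An ADA mechanism is one of the two possibilities named. The monkey thrombocytopenia appeared from 10 to 12 days after the first dose (Section 2.2.2.1), a time that falls inside the 21-day Cycle 1. If the ADA-safety association is run on the IAS, the subjects stopped early for toxicity are the ones missing from it.

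**Working it through.** The plan states no figure for the IAS, so there is nothing to reproduce. The check is a count from the schedules, followed by two illustrations.

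**1. Qualifying samples by doses received** (Tables 1-2 and 1-10; the Cycle 1 Day 1 sample is used as baseline)

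| Doses received | Postbaseline predose ADA samples | Other scheduled ADA samples |
|---|---|---|
| 1 | 0 | up to 3 (discontinuation, SFU1, SFU2) |
| 2 | 1 (Cycle 2) | up to 3 |
| 3 | 2 (Cycles 2, 3) | up to 3 |
| 4 | 3 (Cycles 2, 3, 4) | up to 3 |

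Three is a ceiling. The discontinuation visit may double as SFU1 (Section 7.1), and a subject who starts new anticancer treatment moves to survival follow-up (Section 7.1.1). The zero in the first row assumes that the subject stops before a Cycle 2 Day 1 draw.

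**2. How many DLT subjects could be excluded at one dose level**

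Inputs: n = 9, the maximum per dose level (Section 9.2); DLT rate p = 0.16 and 0.33, the ends of the BLRM target interval (Appendix 8). Assumption: every DLT subject stops before Cycle 2 Day 1.

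- Expected exclusions = n × p: 9 × 0.16 = 1.44; 9 × 0.33 = 2.97.
- Expected to remain in the IAS: 9 − 1.44 = 7.56; 9 − 2.97 = 6.03.
- Chance of at least one exclusion = 1 − (1 − p)^9: 1 − 0.84^9 = 79%; 1 − 0.67^9 = 97%.

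Under that assumption the IAS holds no subject with a DLT, so an ADA-DLT association cannot be estimated in it. Subjects who stop early for other reasons would add to the loss.

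**3. Effect on ADA incidence**

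Let f be the fraction stopping before Cycle 2 Day 1, a the ADA incidence in them and b the incidence in the rest. The IAS reports b, and all sampled subjects would show f·a + (1 − f)·b, so the difference is f·(a − b). The documents give none of these values. All inputs below are assumptions, with f from 10% to 20%:

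| a | b | IAS reports | All sampled subjects |
|---|---|---|---|
| 50% | 10% | 10% | 0.10×0.50 + 0.90×0.10 = 14%, to 0.20×0.50 + 0.80×0.10 = 18% |
| 10% | 10% | 10% | 10% |
| 10% | 50% | 50% | 0.10×0.10 + 0.90×0.50 = 46%, to 0.20×0.10 + 0.80×0.50 = 42% |

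The sign of the bias follows the sign of a − b, which is unknown. Subjects with one dose might have more ADA, if ADA drives the toxicity, or less, because they had less exposure.

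**The case against.** The strongest reply is that the word predose is loose drafting. In both tables the discontinuation and follow-up samples sit in the single ADA row, whose label opens with "Preinfusion (on infusion days". On that reading the preinfusion condition applies on infusion days only, and the IAS text merely echoes the row. The adverse event section also gives a wide window: "On-treatment period: from day of first dose of trial medication to 30 days after last dose of trial medication". A discontinuation sample inside it is on-treatment in time. This is a fair account of what may have been intended, but it does not make the text say so. It also helps only in part: SFU1 at 30 to 35 days falls inside that window only on day 30, and SFU2 at 53 to 67 days falls outside it.

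Four further points limit the concern, and they stand:

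- Not every subject with Cycle 1 toxicity is excluded. A DLT subject may be allowed to continue, a subject held for thrombocytopenia may be redosed (Section 6.7.2.3), and a subject who attends Cycle 2 Day 1, gives the sample and is then held may already have one.
- A reader might infer that the early-stopping subjects' ADA data are lost, or that they are certain to be missing from the ADA-safety analysis. The documents do not support that. Section 9.4.7 provides for listing titers and ties the association to no set. The dose escalation and data monitoring committees review all available data.
- A reader might also infer that ADA is the suspected cause of the main toxicity, so that the bias must run toward no relationship. The protocol says less: ADA is one of two possible mechanisms, in monkeys, and the mechanism is uncertain. The phase 1a clinical signal in Section 2.3.2.1 concerns recent anti-PD-1/PD-L1 exposure, not ADA.
- The analyses are exploratory in purpose (Section 9.1), and the SAP is still to be finalized.

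**Conclusion.** The point holds as a defect of definition. On the literal wording, and for the monotherapy schedules, a subject who stops before a Cycle 2 Day 1 predose draw cannot enter the only defined immunogenicity set, whatever later ADA samples exist. Entry thus depends on early safety outcome. The neighbouring PK set (Section 9.3.5) needs only 1 evaluable sample and has no such restriction.

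ADA incidence, and any ADA-safety association run on the IAS, can be biased; the direction and size are unknown. The only scale available is the illustration of 1.4 to 3.0 DLT subjects out of 9 at a dose level in the target interval, which assumes that all of them stop. The incidence figures rest wholly on assumed rates. The combination schedules are placeholders, so nothing is claimed about them. The text should be changed before the SAP is final.

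**What to change.** In Section 9.3.6 and the SAP, define the IAS as subjects with at least 1 dose of GEN1053, a baseline ADA sample and at least 1 evaluable postbaseline ADA sample at any time, including treatment discontinuation, SFU1, SFU2 and unscheduled visits. In Section 9.4.7, name this set for ADA incidence and for the ADA-safety association.

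A subject who stops after one dose then has up to 3 scheduled qualifying samples instead of none. The cost is a sentence in each section; the samples are already scheduled.

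There is a small downside. Time since last dose will vary more between subjects, which the listing can show. An early discontinuation sample may be drawn at a drug level where the assay cannot detect ADA. Such results should be reported as nonconclusive under the drug-tolerance caveat already in Section 9.4.7 and not counted as negative. That section contrasts positive with non-positive, so the SAP should separate negative from nonconclusive within the second group. The follow-up samples at 30 and 60 days, taken as drug clears, should be less affected.

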9.4 Statistical Analyses

This section is a summary of the planned statistical analyses of the most important endpoints including primary and key secondary endpoints. The SAP will be finalized prior to database lock, and it will include a more technical and detailed description of the statistical analyses described in this section.

Baseline is the last available measurement prior to first dosing of trial treatment, if not otherwise specified.

9.4.1 Subject Demographics and Baseline Characteristics

Demographic and other baseline data including disease characteristics will be listed and summarized descriptively for all subjects, by dose cohort and by indication in Expansion for the FAS.

Relevant medical histories and current medical histories at baseline will be summarized separately by system organ class and/or preferred term, (for all subjects, by dose cohort, and by indication in Expansion).

9.4.2 Efficacy

9.4.2.1 Antitumor Activity Based on RECIST 1.1

RECIST criteria (v1.1) will be used to define response (Eisenhauer et al., 2009). Additional details of RECIST can be found in Appendix 7.

The BOR is the best response recorded from the start of the treatment until PD/recurrence (the smallest measurements recorded will be used as the reference for PD). Subjects with CR or PR are considered to be objective responders. Subjects with CR, PR, or SD are considered to be in disease control. Subjects for whom data are NE are counted as nonresponders.

The best change (maximal reduction in the sum of the diameters in the target lesions) in target lesions at any time on trial will be reported using waterfall plots.

Individual subject data listings and summaries of objective response, best overall tumor response, and disease control will be presented by dose cohort/indication and total.

9.4.2.1.1 Objective Response Rate

The confirmed ORR is defined as the proportion of subjects with BOR of confirmed CR or confirmed PR (ie, "responders"), as per local review and according to RECIST v1.1. Repeat imaging may be performed no less than 4 weeks after the criteria for CR or PR are met to confirm the initial response.

An assessment of SD requires at least 5 weeks from C1D1 to scan date.

9.4.2.1.2 Duration of Response

DoR only applies to subjects whose confirmed BOR is CR or PR and is defined as the time from the first documentation of objective tumor response (CR or PR) to the date of first PD or death due to any cause.

DoR will be censored and summarized in the same way as PFS, see below.

- 9.4.2.2 Exploratory Objectives
- 9.4.2.2.1 Biomarkers

Biomarker analyses in this trial are exploratory and focused on confirming the MoA of GEN1053, identifying potential PD markers to help identify the appropriate dose and schedule of GEN1053, and identifying potential predictive markers that may be further validated in prospective trials with GEN1053.

Expression of biomarkers, such as CD27, **CC** on peripheral immune cell populations, as well as cytokine measurements, will be tabulated for all subjects who have samples collected and testing performed. Biomarker assessments will be summarized by time point using descriptive statistics. Changes in biomarker parameters, as compared to baseline, will be calculated and analyzed for association with relevant clinical endpoints such as objective response, PFS, and OS. Subgroup analyses may be performed to evaluate differences between biomarker parameters in groups of responders and nonresponders or other clinically relevant subgroups, and to evaluate the associations between biomarker parameters and specific clinical endpoints. Univariate and multivariate analyses, as well as pathway analyses, may also be performed if applicable. Any pharmacodynamic measures will be listed, tabulated, and plotted as appropriate. Subjects may be grouped by cohort, dose schedule, or clinical response. Further details will be provided in the SAP.

Results of biomarker analyses may also be presented in a separate report.

9.4.2.2.2 Antitumor Activity Based on iRECIST

Responses assigned using iRECIST (NCCN, 2021a; Seymour et al., 2017) have a prefix of "i" (eg, iCR or iPR, and iUPD or iCPD) to differentiate them from responses assigned using RECIST 1.1. Similar nomenclature is used for iSD, iPFS, iDoR, iDCR, and iORR.

The exploratory analysis methodology is similar to that described in Section 9.4.2.1.

9.4.2.2.3 Progression-Free Survival

PFS is defined as the time from the date of C1D1 to the date of the first documented PD or death due to any cause. PFS will be assessed via local review according to RECIST v1.1 (Eisenhauer et al., 2009). PFS will be censored in accordance with Table C1 in Appendix C in the FDA Guidance for Industry: Clinical Trial Endpoints for the Approval of Non-small Cell Lung Cancer Drugs and Biologics (FDA, 2015).

PFS will be analyzed in the FAS population. The PFS distribution will be estimated using the Kaplan-Meier method, and the Kaplan-Meier curves, medians, and 95% CIs of the medians will be presented for each Expansion cohort.

9.4.2.2.4 Overall Survival

OS is defined as the time from date of C1D1 to date of death due to any cause. If a subject is not known to have died, then OS will be censored at the latest date the subject was known to be alive (on or before the cutoff date).

The OS distribution will be estimated using the Kaplan-Meier method, and the Kaplan-Meier curves, medians, first and third quartiles, and 95% CIs of the medians will be presented for each Expansion cohort.

9.4.2.2.5 Tumor Growth

Prebaseline scans will be collected to explore tumor growth and selected, concomitant prebaseline laboratory data (neutrophils, lymphocytes, platelets, hemoglobin, albumin, and LDH) will be collected to explore their association with tumor growth prior to treatment, and to evaluate drug effect on tumor growth. For this analysis, scans will be centrally read to ensure a consistent reading of prebaseline and on-treatment scans. These central readings will only be used to evaluate the prebaseline and on-treatment change in tumor size based on target lesions. The response to treatment described in Section 9.4.2.1 will be based on investigator readings. The results of this exploratory analysis will be reported in a separate report.

